Since use of low FGF leads to a long time constant, a wash-in phase using a high FGF and high vapouriser concentration (Fv) of volatile anaesthetic is warranted in order to rapidly achieve the required concentration of inhalation anaesthetic in the breathing system.⁸ Conventionally LFA is administered using high flows initially up to 4-10 L/min for 3-time constants (approximately 3 minutes) with Sevoflurane dial setting of 0.8-2.5% to bring the circuit to the desired concentration, then the flows are reduced for maintenance of anaesthesia. In this method of initial high flows, there is risk of delivering high anaesthetic concentrations during induction of anaesthesia and wastage of volatile agents when the total consumption of anaesthetic agent (AA) is calculated at the end of surgery.

Wash-in is the time taken to reach 1 MAC concentration. Sevoflurane wash-in schemes lack simplicity, target coverage and applicability. Various studies have demonstrated that the time to reach 1 MAC decreased at higher flow rates (1-2-4) but plateaued at 4-4.8 L/min. Lindqvist et. al.9 reported a 2-step wash-in technique to achieve a FAS of 1.2%; starting with FGF 1 L·min-1 and FvS 8% for 1 min, then reducing FGF to 1, 0.7, 0.5, and 0.3 L \cdot min-1. They found that the respective time to achieve the target FAS was 1.8, 1.5, 2.5 and 3.6 min. Horwitz et. al.10 reported that by using a FGF of 1.0 or 0.5 L·min-1 with a FvS 6% during the wash-in, the respective time to reach 1 MAC was 6.2 ± 1.3 and 15.2 ± 2.4 min and up to 1.5 MAC at 7.5 ± 2.5 and 19 ± 4.4 min. Shin et al.11 performed a wash-in study using a Primus anaesthetic machine connected to a test-lung, using a FGF of 0.5, 1, and 3 L·min-1 and setting the FvS to 6%. The respective mean time to reach a FAS of 4% for each FGF was 1165, 534, and 155 s. Nel MR et. al. 1_2 have shown while using FGF=6 L (Nitrous Oxide 4L + O₂ 2L) and Sevoflurane vapouriser dial set at 2.5% that equilibration point defined as FE/FI=0.8 (corresponding to FAS=2%) can be reached in a mean (standard deviation) of 8.2 ± 2.1 min. Tribuddharat S et. al.8 studied the 1-1-8 wash-in scheme with FGF=2L (O₂ 1 L + Air 1 L) and FvS 8% which yielded a respective FaS of 1, 1.5, 2, 2.5, 3, and 3.5% at 1, 1.5, 2, 3, 3.5, and 4.5 min when used with N2O and at 1, 1.5, 2, 3, 4, and 5 min when used with air.

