In a test lung model study Jakobsson et. al.4 reported wash-in with a respective FGF of 0.3 and 4 L·min-1 and a FvS of 8%. They found that the FaS reached 1 MAC (2.1%) at 547 ± 83 and 38 ± 6 s, respectively. It was possible to increase the AA concentration from 0 to 1 MAC value in around one minute by using a FGF of 4–4.8 L/min using a fixed dial setting of 3 MAC, but raising the FGF further did not result in shorter wash-in times. Wash-in times were significantly faster with higher flow rates for FGF spanning from 1, 2 and 4 L/min, however a plateau started at FGF 4–4.8 L/min, where increasing the FGF further up to 6 or 8 L/min did not shorten the time to reach 1 MAC significantly.¹³

The conventional method which uses initial high FGF during the wash-in phase defeats the purpose of LFA such as conservation of gases, reduced environmental pollution and economical savings even

though it provides a more stable gas composition within the breathing system. Beginning of anaesthesia is also a task-intense phase requiring multiple tasks to be performed to ensure the patient safety. Any additional tasks during this phase may have high chances of being forgotten with a potential for compromised patient safety. Therefore, the technique has to be simple to execute. We wish to evaluate a technique of initiating Sevoflurane LFA which is simple, has a quick wash-in and minimises gas consumption without compromising the safety when compared to conventional method of attaining LFA using initial high flows.

Methods

After obtaining the approval from the Institutional Ethics Committee of The Royal Hospital, Muscat, we will register this prospective, randomised, descriptive study in an appropriate online clinical trial registry. A written informed consent will be obtained from all the patients. Forty-eight patients of either gender aged 18-65 years, with American Society of Anesthesiologists (ASA) physical status of 1-2, undergoing elective surgery with the expected duration more than 1 hour under general anaesthesia requiring endotracheal intubation will be included. Pregnant women, smokers, patients with a body mass index (BMI) \geq 30 kg/m₂, cardiac/pulmonary/renal or liver impairments, upper or lower respiratory infections within the past 6 weeks and anticipated difficult airway will be excluded.

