Sample size is calculated based on a previous study₈ which showed the 1-1-8 wash-in scheme with FGF=2L (O₂ 1 L + Air 1 L) and Sevoflurane dial at 8% yielded an F_AS of 2% at 2 ± 0.5 min. Hence, we assume that with our wash-in technique using FGF=0.5 L (O₂ + Air) and FvS 8% the time needed to reach F_AS=2% will be around 8 min. To detect a difference of 2 min (25%) with standard deviation (SD) of 2 using an alpha level of 0.05 and a power of 0.90 the sample size needed is 22 per group. For a possible 10% dropouts, it is decided to include 24 patients per group.

Statistical analysis will be carried out using an appropriate statistical software. Data will be presented as mean \pm SD or median (range). Intergroup differences will be assessed for significance using Student's t, Kruskal-Wallis, chi-squared or Fisher exact tests, as appropriate. P < 0.05 will be considered statistically significant.

Study duration: Approximately 8 months (from December 2023 to July 2024). Data collection: December 2023-May 2024, statistical analysis and writing manuscript: June-July 2024.

How will the expenses be met with? : Does not involve any additional expenditure.

Department associated in the study: Department of Anaesthesia and Intensive Care, Royal Hospital, Muscat.

References

1. Baum JA. Low-flow anesthesia: theory, practice, technical preconditions, advantages, and foreign gas accumulation. J Anesth. 1999;13(3):166-74. doi: 10.1007/s005400050050. PMID: 14530937.

4. Jakobsson P, Lindgren M, Jakobsson JG. Wash-in and wash-out of sevoflurane in a test-lung model:
A comparison between Aisys and FLOW-i. F1000Res. 2017 Mar 29;6:389. doi: 10.12688/f1000research.11255.2. PMID: 28529707; PMCID: PMC5414818.

5. Feldman JM. Managing fresh gas flow to reduce environmental contamination. Anesth Analg. 2012 May;114(5):1093-101. doi: 10.1213/ANE.0b013e31824eee0d. Epub 2012 Mar 13. PMID: 22415533.

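### One SD is assumed for both arms and Student's t is the only parametric test named, although the protocol gives reason to expect unequal spread; naming Welch's t is a small, nearly free improvement

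*Protocol*

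**What the plan says.** The Statistical analysis section starts from a cited result of 2 ± 0.5 min at 2 L/min and assumes for the over-pressure arm (OP, 0.5 L/min, dial 8%) that "the time needed to reach F_AS=2% will be around 8 min". The size is then set "To detect a difference of 2 min (25%) with standard deviation (SD) of 2", and "using an alpha level of 0.05 and a power of 0.90 the sample size needed is 22 per group". No expected mean or SD is given for Group C (6 L/min, dial 3%).

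For the analysis, "Intergroup differences will be assessed for significance using Student's t, Kruskal-Wallis" and two tests for categorical data, each where suitable. No unequal-variance test is listed, and the variance form of the t test is not stated.

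The Introduction reports wash-in times with SDs at different flows, among them "the respective time to reach 1 MAC was 6.2 ± 1.3 and 15.2 ± 2.4 min" for 1.0 and 0.5 L/min, and, in a test lung, "at 547 ± 83 and 38 ± 6 s, respectively" for 0.3 and 4 L/min.

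**The concern.** The two arms start at flows that differ twelve-fold (6 v 0.5 L/min), and the primary outcome is a time that depends on flow. If SD grows with the mean, arms that differ in mean will not share one SD. The pooled standard error then weights the two variances wrongly whenever the numbers analysed differ: it is too small if the more variable arm loses more patients and too large in the reverse case. Falling back on the listed rank test does not settle this, because a rank test also responds to a difference in spread. At stake are the coverage of the interval for the difference in T_target, the analysis of gas consumption, and the clarity of the planning assumption.

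**Working it through.** **1. The plan's own figure.** Difference 2, SD 2 in both arms, two-sided alpha 0.05 (two-sided is assumed; one-sided would give 18), power 0.90:

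n = 2 × [SD × (1.960 + 1.282) / difference]² = 2 × 3.242² = 21.0, rounded up to 22. Exact noncentral-t power at 22 per group is 0.900. The stated size reproduces.

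**2. Does SD follow the mean in the cited data?** Within studies that compare two flows:

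| Cited comparison | Faster | Slower | SD ratio |
|---|---|---|---|
| 1.0 v 0.5 L/min, to 1 MAC | 6.2 ± 1.3 min | 15.2 ± 2.4 min | 1.85 |
| 1.0 v 0.5 L/min, to 1.5 MAC | 7.5 ± 2.5 min | 19 ± 4.4 min | 1.76 |
| 4 v 0.3 L/min, test lung | 38 ± 6 s | 547 ± 83 s | 13.8 |

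All three rise. Across all eight cited pairs (adding 2 ± 0.5 and 8.2 ± 2.1 min) the trend is strong but not strict: Spearman 0.83, coefficient of variation (CV) 0.15 to 0.33.

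**3. What SD ratio follows for T_target?** Take SD 2 in OP. For Group C use CV 0.25 (0.5/2), except in the row with a cited SD:

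| Group C time (assumption) | Basis | Group C SD | Larger/smaller SD |
|---|---|---|---|
| 8.2 min | cited study at 6 L/min, dial 2.5% | 2.1 | 1.05 |
| 10 min | 8 + 2 | 2.5 | 1.25 |
| 6 min | 8 − 2 | 1.5 | 1.33 |
| 3 min | Introduction's approximate time for conventional high flow | 0.75 | 2.7 |
| 2 min | 9-10 L reserve volume at 6 L/min | 0.5 | 4 |

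For the last row, the time constant is 9/6 to 10/6 = 1.5 to 1.67 min. Reaching two-thirds of the dial (2% of 3%) takes ln 3 = 1.10 time constants, so 1.6 to 1.8 min without uptake, or roughly 2 min if uptake adds a little (assumption). The range is therefore about 1.0 to 4.

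**4. Gas consumption.** Counted from T_zero to T15, oxygen plus air in OP is 0.5 × 15 = 7.5 L for every patient. In Group C it is 6T + 0.5 × (15 − T) = 7.5 + 5.5T litres, where T is T_target. Its SD is 5.5 × SD(T): 2.75 L if SD(T) = 0.5 min, 8.25 L if SD(T) = 1.5 min. The spread is unequal by design, in favour of a larger SD in Group C.

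**5. How often does the 95% interval for the mean difference miss?** Simulated normal data, OP SD 2, one million trials per cell:

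| Group C SD | OP v C analysed | Student | Welch |
|---|---|---|---|
| 0.5 | 22 v 22 | 5.5% | 5.0% |
| 0.5 | 20 v 24 | 7.6% | 5.0% |
| 0.5 | 24 v 20 | 3.7-3.8% | 5.0% |
| 1.5 | 22 v 22 | 5.1% | 5.0% |
| 1.5 | 20 v 24 | 5.6% | 5.0% |
| 2.1 | 20 v 24 | 4.9% | 5.0% |

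**6. Cost of Welch and a note on power.** At 22 per group and SD 2 in both arms, simulated power is 0.900 (Student) and 0.899 (Welch). With SD proportional to the mean, noncentral-t power for 2 min is 0.956 if Group C is 6 ± 1.5 and 0.817 if it is 10 ± 2.5.

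**The case against.** The strongest counter-case has four parts.

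- **The ratio is not in the documents.** A reader might infer that the arms must differ about four-fold in SD. That needs a Group C time of about 2 min, which the protocol never states. The plan's own 2-min difference implies 1.25 to 1.33, and the cited study nearest to Group C's flow and dial gives 1.05, though its endpoint was an equilibration ratio, with 2% at 80% of the dial setting rather than 67%. This stands. So does the limit on the cited data: 7.5 ± 2.5 has a larger SD than 8.2 ± 2.1 or 15.2 ± 2.4, so the pattern holds within studies, not in every comparison.
- **Error rates under the null.** If SD is proportional to the mean, equal means imply equal SDs, and Student's t keeps its level even at 20 v 24 (5.0%). This stands. The figures in the table are therefore best read as interval non-coverage when the means differ, not as an inflated false-positive rate for the primary test. With a difference of several minutes either test would detect it.
- **Unequal losses are hypothetical.** Allocation is in blocks, 24 per group, with 10% dropout allowed. A 20 v 24 split means 17% lost in one arm and none in the other, and nothing in the protocol predicts that. This stands and limits the size.
- **Pooled variance is not prescribed.** The tests are listed for use where suitable, and a SAP that is not shown may fix the variance form. This stands in part: the list leaves the choice open, but offers no unequal-variance test to choose.

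None of this touches gas consumption, where unequal spread after T_zero follows from the flow settings alone.

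**Conclusion.** The point holds as a minor one. One SD for both arms sits poorly with the protocol's own same-study data and with the design of the gas-consumption outcome, and the only parametric test named is the one usually computed with pooled variance. With equal completers the effect is at most about half a percentage point of coverage. It reaches 7.6% or 3.7-3.8% non-coverage only at four-fold SDs with a 20 v 24 split. These figures rest on normal data and on an assumed SD ratio within about 1.0 to 4.

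A reader might also infer that the stated power is wrong. It is not: 0.90 is correct under the common SD of 2. The values 0.96 and 0.82 show only what proportional SDs would give. Nor do the documents say how the SD of 2 was obtained; it equals 4 × 0.5, matching 4 × 2 = 8 min, but that derivation is an inference.

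**What to change.** In the Statistical analysis section, name Welch's unequal-variance t test, with the 95% CI for the difference in means, for T_target and the other continuous outcomes compared by means. Analysing log T_target and reporting a ratio of geometric means is an option if a constant CV seems the better description; the result is then a ratio rather than minutes.

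It would also help to state the expected mean and SD for each arm beside the sample size, with the power that follows. Welch's test does not supply that assumption.

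The cost is one or two sentences. The sample size need not change, and Welch loses about 0.1 point of power if the SDs turn out equal.

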Volatile anaesthetic agents are unique in that it is possible to significantly reduce the mass of drug delivered to the circuit (by lowering FGFs) without altering the amount that actually enters the patient.⁶ Studies have shown that 1 L/min change in FGF with Sevoflurane results in a change of between 4 and 18 ml/hour consumption of sevoflurane.⁷ The challenge is to control the dynamic equilibrium of FG composition as the uptake and metabolism are time-sensitive and many factors influence the consumption and production of gaseous components. This can be achieved only through frequent adjustments in the gas flow controls.¹

LFA requires flow meters calibrated to low flow down to 50 ml/min, leak-proof circle breathing system and airway devices like cuffed endotracheal tube (ETT), gas monitoring system providing inspired and end-tidal concentrations of agent, vapourisers capable of delivering high concentrations and calibrated to be accurate at low FGF. Since low FGFs are added to significantly large reserve volume (approximately 9-10 litres), consisting of breathing tubing, reservoir bag, anaesthetic ventilator, intergranular space, etc., in addition to functional residual capacity (FRC) of the patient, it requires 3time constants (calculated by reserve volume divided by FGF) to effect 95% change in gas composition to occur. However, once steady state is achieved, LFA provides the most economic use of anaesthetic agents. Sevoflurane when used with strong base-free CO₂ absorbent is suitable for use in LFA because it has low blood-gas solubility. The minimum alveolar concentration (MAC) of Sevoflurane varies with patient age, from 1.4% at age 80 years to 2.3% at age 1 year.8 The optimal alveolar concentration of Sevoflurane (FAS) to prevent motor movement and autonomic response during anaesthesia is MAC-Bar which approximates 1.5 MAC. Thus, the target of FAS during anaesthesia in daily practice varies between 1 to 3.5%, depending on the adjuvant drugs used.

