Age, gender, height and weight of the patients will be recorded. All the patients will follow the standard fasting requirements and receive no sedative premedication. They will be randomised before entering the operating room into one of the two groups, 'conventional group' (Group C) and 'over-pressure group' (Group OP), using block randomisation technique with varying block sizes. An appropriate intravenous cannula will be secured in the operating room and Ringer's Lactate 500 ml will be started. The patients will receive standard anaesthetic care and intra-operative monitoring with electrocardiogram, pulse oximeter (SpO₂), non-invasive blood pressure (NIBP) and capnography. Avance CS₂ anaesthesia workstation (GE Healthcare, Madison, WI, USA) which has an integrated anaesthetic gas analyser, displays age-adjusted MAC according to the internal algorithm and returns sampled gas to the breathing system will be used in this study. The breathing system will consist of a 2 L reservoir bag, disposable breathing circuit, heat-moisture exchanger and standard circle system with Sodalime as the CO₂ absorbent. The workstation will be tested to ensure no leak in the system and vapourisers are calibrated.

Ideal Body Weight (IBW) of the patient will be calculated based on the following formula: IBW (kg)=50 + 0.91 (height in cm – 152.4) for Men and 45.5 + 0.91 (height in cm – 152.4) for Women. The ventilator will be preset in Pressure Control-Volume Guarantee (PCV-VG) mode with a tidal volume of 8 ml/kg of IBW, respiratory rate=14 breaths/min, positive end-expiratory pressure (PEEP)=5 cmH₂O and an inspiratory:expiratory ratio of 1:2. The set minute volume will be noted. The alarm for end-tidal Sevoflurane (FAS) will be set at 2% to alert the clinician.

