Consumption of gases (Oxygen, Air and Sevoflurane) from the beginning until T₁₅ will be retrieved. Any reduction in mean BP >20% from the baseline will be treated with intravenous Ephedrine 12 mg bolus and consumption of Ephedrine will be noted. Expired minute volume (MV_E) at T_{target} and T₁₅ will be noted. The study period will end at T₁₅ in both the groups. Painting the surgical parts and draping will be permitted during the study period. Care will be taken to avoid any activity which risks ETT disconnection during the study period. Subsequent management of anaesthesia will be left to the discretion of the attending Anaesthesiologist.

For both the groups, 'stability of Sevoflurane concentration', defined as FAS in the target range of 1.6-2.4% during the time interval from T_{target} till T₁₅ will be assessed. The investigator will be allowed during this period to increase or decrease if needed the vapouriser dial by 1% at a time every 2 min to keep the FAS in the target range. The number of times the vapouriser dial is adjusted will be noted. The system will be considered 'stable' if the FAS is maintained in the target range without the need for dial adjustment and 'unstable' if vapouriser dial adjustment is needed at any time during this period.

Delivery of Oxygen will be monitored to ensure at least 300 ml/min and delivered F_1O_2 at least 0.3 at all time. The investigator will be allowed to increase if needed the set F_1O_2 by 0.1 at a time every 2 min to keep the delivered $F_1O_2>0.3$. The number of times the set F_1O_2 is adjusted will be noted. End-tidal carbon dioxide (ETCO₂) will be maintained between 30 and 40.

The aim of the study is to assess during the wash-in phase of LFA the feasibility of the method, stability of the system and consumption of gases. The primary outcome will be the time required to achieve FAS 2%. Secondary outcomes will be the stability of the system assessed by the number of times vapouriser dial and the set F1O₂ adjusted, consumption of gases and of ephedrine.

Statistical analysis

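### The listed tests for time to end-tidal sevoflurane 2% are all unadjusted; prespecifying one baseline body-size covariate is a cheap improvement, with a gain that depends on an R² the protocol does not give

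*Protocol*

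**What the plan says.** On the primary outcome, Methods states "The primary outcome will be the time required to achieve FAS 2" (per cent). It is measured in seconds from T_zero, the opening of the vapouriser, and is called T_target.

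On the analysis, the Statistical analysis section states "Intergroup differences will be assessed for significance using" one of four tests, chosen as appropriate: Student's t, Kruskal-Wallis, chi-squared or Fisher exact. No test is tied to a particular outcome and no covariate is mentioned. Randomisation (Methods) is in blocks of varying size, with no stratification factor.

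On baseline data, Methods states "Age, gender, height and weight of the patients will be recorded" and, after describing the ventilator preset, "The set minute volume will be noted". The preset is 8 ml per kg of ideal body weight at 14 breaths/min, and ideal body weight is calculated from height and sex.

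The sample size (Statistical analysis) rests on a difference of 2 min "with standard deviation (SD) of 2", alpha 0.05 and power 0.90. This gives 22 per group, raised to 24 for dropouts.

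**The concern.** Neither the randomisation nor the listed tests make any use of patient characteristics, although the protocol gives a reason to expect that body size matters. The Introduction counts the patient's functional residual capacity in the volume that determines the circuit's time constant, and preset ventilation scales with height and sex. If body size explains part of the spread in T_target, an unadjusted test leaves that part in the error term.

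At stake is the width of the interval for the primary difference, and some power in a trial planned at 0.90 with two spare patients per arm. There is also a smaller, practical benefit. If two arms of about 22 happen to differ in body size, a covariate named in advance removes the temptation to choose one after seeing the data.

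**Working it through.** **Inputs from the protocol.** Difference δ = 2 min, SD = 2 min, alpha 0.05, power 0.90, 22 evaluable per group (N = 44). Sidedness is not stated. Two-sided is assumed because it reproduces 22; one-sided gives 18.

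**Input not in the protocol.** The share of within-arm variance in T_target explained by baseline covariates (R²). Values of 0 to 0.3 are assumed.

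**Step 1: reproduce the plan's figure.** n = 2 × (1.960 + 1.282)² × 2²/2² = 21.01, so 22 per group, as stated. With the t distribution, power at 22 is 0.8997. The 95% CI half-width is t(0.975; 42) × 2 × √(2/22) = 2.018 × 0.603 = 1.22 min.

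**Step 2: are the covariates legitimate?** Age, sex, height and weight cannot be affected by allocation. Set minute volume is noted in the operating room, after randomisation, but it is fixed by a formula: 8 × 14 = 112 ml/min per kg of ideal body weight. For men it is 0.112 × [50 + 0.91 × (height − 152.4)] L/min; for women 45.5 replaces 50. It therefore depends on height and sex only, and is described before T_zero. Expired minute volume is different: it is recorded at T_target and at T15, after the allocated settings have started, and the first of those times is itself the outcome.

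**Step 3: redundancy.** Since set minute volume is an exact linear function of height and sex, a model with an intercept, age, sex, height, weight and set minute volume has 6 columns but rank 5. Set minute volume can stand in for height and sex, but cannot be entered with both.

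**Step 4: expected power and precision with k covariates.** Adjustment reduces the residual SD to 2√(1 − R²). It costs k degrees of freedom and, on average, inflates the variance through chance imbalance by c = (N − 3)/(N − k − 3).

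- SE = 2 × √(1 − R²) × √c × √(2/22), with df = 42 − k.
- Power comes from the noncentral t distribution with noncentrality 2/SE; half-width = t(0.975; df) × SE.

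Example: k = 1, R² = 0.2, c = 41/40 = 1.025. SE = 2 × 0.894 × 1.012 × 0.3015 = 0.546; noncentrality 3.66; half-width 2.0195 × 0.546 = 1.10 min; power 0.947.

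| Covariates | c | R² = 0 | 0.1 | 0.2 | 0.3 | Break-even R² |
|---|---|---|---|---|---|---|
| None | – | 0.900 (1.22) | – | – | – | – |
| 1 | 41/40 | 0.892 (1.23) | 0.921 (1.17) | 0.947 (1.10) | 0.969 (1.03) | about 0.03 |
| 2 | 41/39 | 0.884 (1.25) | 0.914 (1.19) | 0.942 (1.12) | 0.965 (1.05) | about 0.05 |
| 3 | 41/38 | 0.876 (1.27) | 0.907 (1.20) | 0.936 (1.13) | 0.961 (1.06) | about 0.08 |
| 4 | 41/37 | 0.867 (1.29) | 0.899 (1.22) | 0.930 (1.15) | 0.956 (1.08) | about 0.10 |

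Cells show power, with the CI half-width in minutes in brackets. R² is the total explained by all covariates in that row.

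The figures assume approximate normality, one SD for both arms and model-based standard errors.

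**The case against.** The strongest case against the point is that nothing here is wrong. Under randomisation the unadjusted test is valid, and its error rate and interval already allow for chance imbalance. The sample size was computed for that same comparison and reproduces. The list of tests is a menu to be used as appropriate, and a statistical analysis plan that is not shown could still add an adjusted model. All of this stands. It is why the point is an improvement to a written method and not a defect.

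A reader might go further and infer that precision is certainly being lost. The protocol does not support that. It gives no correlation between any baseline variable and T_target. The Introduction's remark that "many factors influence the consumption and production of gaseous components" concerns gas composition in general and names neither body size nor minute volume. Low R² is plausible: a BMI of 30 kg/m² or more and cardiac, pulmonary, renal or liver impairment are exclusions, and ventilation is standardised to ideal body weight. Later ventilation may also move away from the preset, since end-tidal CO₂ is to be kept within a range. With no explained variance, adjustment loses a little power.

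A reader might also infer that all five recorded variables should be used, or that the unadjusted result would be biased. The first fails on redundancy and on the rising cost shown in the table. The second fails because allocation is random.

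**Conclusion.** The point holds as a low-cost improvement. The tests that could apply to T_target are both unadjusted, and a legitimate baseline covariate with a plausible mechanism is already being collected.

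For one covariate at 22 per arm, power would move from 0.900 to between 0.892 and 0.969, and the half-width from 1.22 min to between 1.23 and 1.03 min, as R² runs from 0 to 0.3. The worst case is a loss of about 0.01 in power. With three covariates it is about 0.024, so a sparse model is the safer choice. The size of the gain, and even its sign, rests on an assumed R².

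**What to change.** Add one sentence to the Statistical analysis section: T_target will be analysed by linear regression on group and set minute volume (the preset value), optionally with age; the adjusted difference will be reported with a 95% CI from heteroscedasticity-robust standard errors in a small-sample form; and the unadjusted test will be a sensitivity analysis.

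Robust errors are sensible because the two arms start at very different gas flows. The Introduction's own literature figures show the SD of time to 1 MAC changing with flow: 1.3 min at 1.0 L/min against 2.4 min at 0.5 L/min.

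Do not enter set minute volume together with both height and sex, and do not adjust for expired minute volume. Choose the covariates before any outcome data are examined.

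The cost is that sentence and, if the covariate proves uninformative, about 0.01 in power (about 0.016 if age is also entered and explains nothing). No additional data or patients are needed, and the sample size can stay as it is.
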